12.3 Visual Acuity

The visual acuity scores will be converted to logMAR scale for analyzing change from baseline. LogMar scale is computed as $\text{logMAR} = -\log(\text{visual acuity score in decimal scale})$.

Visual Acuity Score	Decimal Scale	LogMAR Scale
20/20	1.00	0.00
20/25	0.80	0.10
20/30	0.70	0.18
20/40	0.50	0.30
20/50	0.40	0.40
20/70	0.29	0.54
20/100	0.20	0.70
20/200	0.10	1.00
20/400	0.05	1.30
20/800	0.03	1.60

In logMAR scale, lower scores correspond to better vision, and as acuity becomes worse, the value of the logMAR increases.

Worst logMAR score is defined to be the highest value of logMAR scores measured on left and right eyes at a given time point. The changes in worst logMAR score from baseline to Days 1, 4, 7, 10, 14, 15, Days 1-15 combined (i.e. most worst logMAR score on any Days 1-15), 28, 42, and Days 28-42 combined (i.e. most worst logMAR score on any Days 28-42) will be summarized by treatment group using descriptive statistics.

Additionally, the changes in worst logMAR score from Days 1-15 combined to Days 28-42 combined will be summarized similarly as described above.

The International Classification of Diseases 11 [ICD-11, 2018] classifies for distance vision impairment is as follows:

Classification of Vision Impairment	Distance Visual Acuity
Normal	Equal to or better than 20/40
Mild	Worse than 20/40 and equal to or better than 20/70

Moderate	Worse than 20/70 and equal to or better than 20/200
Severe	Worse than 20/200 and equal to or better than 20/400
Blindness	Worse than 20/400

The highest classification of vision impairment of left and right eyes at the given time point will be selected for the analysis. The frequency and proportion of participants for each level of the classification of vision impairment at baseline, Days 1, 4, 7, 10, 14, 15, Days 1-15 combined (i.e. worst vision impairment at any Days 1-15), 28, 42, and Days 28-42 combined (i.e. worst vision impairment at any Days 28-42) will be summarized by treatment group. For the by-time point summary, the denominator for the proportion is the number of participants with visual acuity assessment at the given time point.

The frequency and proportion of participants for each level of the classification of vision impairment at baseline that transitioned to a level of the classification of vision impairment at Days 1, 4, 7, 10, 14, 15, Days 1-15 combined (i.e. worst vision impairment at any Days 1-15), 28, 42, and Days 28-42 combined (i.e. worst vision impairment at any Days 28-42) will be provided by treatment group. For the by-time point summary, the denominator for the proportion is the number of participants with non-missing values at baseline and the given post-baseline time point.

Additionally, the transition of levels of classification of vision impairment from Days 1-15 combined to Days 28-42 combined will be summarized similarly as described above.

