Assess the impact on heart rate, blood pressure and ECG profile of each dose regimen of TBA-7371 and of HRZE over the 14-day treatment period.	
From Day 1 through Day 15:
 
 Mean and frequency distribution of changes in heart rate (HR), systolic blood pressure (SBP) and diastolic blood pressure (DBP) as measured by the following 2 (BP) or 3 (HR) methods: 
 manual (vital signs), after at least 10 minutes in supine position (“manual, supine”);

Objectives	Endpoints
	
 ▪ manual, after 2 (± 0.5) minutes in standing position (“manual, 2-min standing”); ▪ HR from ECG, supine position (“ECG, supine”) • Frequency of participants with $\ge 25\%$ increase in HR, decrease in SBP, decrease in DBP vs. baseline as measured with any of the methods described above. • Mean and frequency distribution of percentage of days with $\ge 25\%$ increase in HR, decrease in SBP, decrease in DBP vs. baseline. • Mean/median change from screening through Day 15 in PR, RR, QRS, QT, QTcF values from baseline ECG.
Assess whether there is tachyphylaxis over the 14-day treatment period for HR, SBP, DBP and eye symptoms.	
 • Mean change in HR, SBP and DBP from Day 1 to Days 4, 7, 10, 14 and 15 for each of the measurement methods described above. • Change in frequency of participants with eye symptoms (all, severe, serious) and change in mean visual acuity score and frequency of color vision abnormalities (tritan, protan, deutan) in one or both eyes and degree of severity (mild, moderate, and severe) from Day 1 to Days 4, 7, 10, 14 and 15.
Assess whether cardiovascular and/or ophthalmic AEs persist or recur up to 4 weeks after discontinuation of treatment with TBA-7371.	
 • Mean change in HR, SBP and DBP from screening to Days 28 and 42 and from Day 14 to Days 28 and 42 for each of the measurement methods described above. • Change in frequency of participants with eye symptoms (all, severe, serious) and change in mean visual acuity score and frequency of color vision abnormalities (tritan, protan, deutan) in one or both eyes and degree of severity (mild, moderate, and severe) from screening to Days 28 and 42 and from Days 1-15 (combined) to Days 28-42 (combined).

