2.3. Benefit/Risk Assessment

In this trial patients with untreated, drug-sensitive pulmonary TB will receive for 14 days either the test drug TBA-7371 in 1 of 5 regimens (from 100 mg QD to 400 mg QD) or commercial HRZE fixed combination (Rifafour® e-275) as control drug, dosed as recommended in the package insert.¹

HRZE is a first line treatment for drug sensitive TB with a well-established, generally favorable, yet not straightforward, benefit-risk profile. The most common AEs associated with HRZE are peripheral neuropathy, optic neuritis, hepatitis, and gastro-intestinal AEs (see Package Insert¹ and 2018 Safety Update² enclosed in study specific manual(s)).

TBA-7371 was tested in adult healthy volunteers in 1 clinical trial (TBA7371-001), composed of three parts: a single ascending dose (SAD) part where single doses from 100 to 800 mg were

tested, a multiple ascending dose (MAD) part where 100, 200 and 400 mg QD were taken for 14 days and a drug-drug interaction (DDI) part. The most common treatment-emergent adverse events (TEAEs) were increase in heart rate associated with decrease in blood pressure and eye symptoms (blurred vision, photophobia, altered color vision, increased lacrimation). The frequency of such events was dose related, starting at doses above 100 mg /day. Most were mild and transient. In particular, vision-related AEs were of short duration, resolved before the next dose and were not persistent changes. Furthermore, tachyphylaxis to changes in heart rate and blood pressure appeared to occur in the MAD part of the trial.

The eye symptoms appeared to be associated with C_{max} . It is therefore possible that the tolerability profile could improve with fractionation of the daily dose. This justifies the inclusion of the BID and TID dosing regimens in this trial.

There is no information on the efficacy of TBA-7371 in humans. PK/PD modelling from animal experiments, supplemented with additional PK data from healthy human subjects, suggests that bactericidal effect could be present at 100 mg/day and then increase with dose.

More information on TBA-7371 is provided in the Investigator Brochure.

The overall risks associated with TBA-7371 at or below 400 mg QD are considered low and are mitigated by the following design features of the present protocol:

- throughout the 14-day Treatment Phase eye symptoms, visual acuity and color vision, ECG will be assessed/recorded every 3-4 days, vital signs daily;

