
8.3.7. Eye Assessment

On each eye assessment day participants will undergo the following 3 eye assessment procedures (always in this order):

- i) Eye symptom assessment using the standardized script provided in Section 10.5 (Appendix 5)
- ii) Visual acuity test by means of the Rosenbaum Pocket Eye Screener on each eye.
- iii) Color vision by means of the Waggoner Computerized Color Vision Test on each eye.

The visual acuity test and Waggoner Computerized Color Vision Test (updated computerized version of the paper-based ColorDX test) will be conducted by staff members trained by an ophthalmologist. Whenever possible the same staff member should conduct all eye assessment procedures on an individual participant.

Details on use of the Rosenbaum Pocket Eye Screener and Waggoner Computerized Color Vision Test are provided in the study specific manual(s).

The 3 eye assessment procedures will be conducted on each of the eye assessment days as follows:

Screening Phase

Once in the AM.

This assessment will be used to assess eligibility (Exclusion Criteria, Section 5.2).

Study Treatment Phase

On Days 1, 4, 7, 10 and 14, 2.5 hours after the 1st daily dose of study drug (see Table 4).

Follow-up Phase

On Days 15, 28 and 42 during scheduled visit.

Early withdrawal visit

If the participant withdraws from the study between Day 1 and 14.

Regarding eye symptoms, based on the outcome of study TBA7371-001, special attention will be paid to blurred vision, photophobia, altered color vision and increased lacrimation, but any other eye symptom will be assessed if it occurs (see Section 10.5, Appendix 5).

Intensity (severity) grading of eye symptoms reported in Section 10.4 (Appendix 4, page 20) may help the investigator. However, the investigator is not obliged to follow these criteria and his/her medical judgement should prevail. The visual acuity and color vision tests will complement the clinical assessment of eye symptoms in the assessment of AE intensity and seriousness.

Any eye symptom and/or abnormal visual acuity / color vision test outcome considered clinically meaningful by the investigator must be recorded as AE.

Participants with eye symptom-related AE classified as severe (\geq Grade 3) and/or serious will contribute to the primary safety end-point (see Section 3.1, Table 5).

Participants with any eye symptom will contribute to secondary safety end-points (see Section 3.2, Table 6).

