12.2 Eye Symptoms

Analysis of eye symptom-related AEs for all eye symptoms, severe eye symptoms, and serious eye symptoms will be based on new events that occurred after Screening. Severe eye symptoms are events that are assigned with grade 3 intensity or greater.

The frequency distribution of participants who experienced 1, 2, or ≥ 3 eye symptom-related AEs in one or both eyes during Day 1 to Day 15 will be summarized by treatment group for all eye symptoms, severe eye symptoms, and serious eye symptoms. The frequency and proportion (expressed in percent) of participants and 95% CI for proportions will be provided for the summary. For computing proportions, the denominator is the number of participants in the Safety population for the given treatment group.

Additionally, the frequency of symptom-related AEs and frequency and proportion (expressed in percent) of participants with eye symptom-related AEs in one or both eyes will be provided by PT and by treatment group for the following:

- All eye symptoms
- Severe eye symptoms
- Serious eye symptoms
- The frequency and proportion of participants with eye symptom-related AEs in one or both eyes that observed at Days 1, 4, 7, 10, 14, 15, Days 1-15 combined (i.e. any eye symptom-related AE observed on any Days 1-15), 28, 42, and Days 28-42 combined (i.e.

any eye symptom-related AE observed on any Days 28-42) will be provided by treatment group for the following: All eye symptoms

- Severe eye symptoms
- Serious eye symptoms

For the by-time point summary, the denominator for the proportion is the number of participants with eye symptom assessment at the given time point.

Any day that a participant reported an eye symptom-related AE in one or both eyes after screening will be counted toward the number of days of having eye symptoms in the study for that individual. Number of days of having eye symptoms will be summarized by treatment group using descriptive statistics for the following:

- All eye symptoms
- Severe eye symptoms
- Serious eye symptoms

Additionally, categorical number of days of having eye symptoms for participants with these events will be summarized by treatment group as follows:

- 1-3 days
- 4-6 days
- 7-9 days
- 10-12 days
- 13-15 days
- ≥ 16 days

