12.4 Color Vision

The three color vision deficits are deutan, protan, and tritan. The degree of severity of color vision deficit is graded as normal, mild, moderate, or severe. The severity of color vision abnormality will be assigned to the highest degree of severity of the 3 color vision deficits. For example, the severities of deutan, protan, and tritan are mild, moderate, normal, respectively, for one of the eyes. For this case, moderate will be assigned as the highest level of severity for color vision abnormality.

The highest level of severity of color vision abnormality of left and right eyes at the given time point will be selected for the analysis. The frequency and proportion of participants for each level of the severity of color vision abnormality at baseline, Days 1, 4, 7, 10, 14, 15, Days 1-15 combined (i.e. worst color vision abnormality at any Days 1-15), 28, 42, and Days 28-42 combined (i.e. worst color vision abnormality at any Days 28-42) will be summarized by treatment group. For the by-time point summary, the denominator for the proportion is the number of participants with visual acuity assessment at the given time point.

The frequency and proportion of participants for each level of the severity of color vision abnormality at baseline that transitioned to a level of the severity of color vision abnormality at Days 1, 4, 7, 10, 14, 15, Days 1-15 combined (i.e. worst color vision abnormality at any Days

1-15), 28, 42, and Days 28-42 combined (i.e. worst color vision abnormality at any Days 28-42) will be provided by treatment group. For the by-time point summary, the denominator for the proportion is the number of participants with non-missing values at baseline and the given post-baseline time point.

Additionally, the transition of levels of severity of color vision abnormality from Days 1-15 combined to Days 28-42 combined will be summarized similarly as described above.

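### The Days 1-15 to Days 28-42 contrast for visual acuity, vision-impairment class and color vision sets the worst of six checks against the worst of two, so with ordinary test variation an unchanged deficit shows, on average, apparent partial improvement.

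*SAP*

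**What the plan says.** One secondary safety objective asks whether cardiovascular or ophthalmic effects persist or recur in the four weeks after TBA-7371 stops. For the eye measures, Protocol 1.1.4.2 (Table 2) specifies changes from screening to Days 28 and 42, and also "from Days 1-15 (combined) to Days 28-42 (combined". For heart rate and blood pressure, the same objective uses Day 14 to Days 28 and 42, with no pooled window.

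Protocol 8.3.7 schedules the eye checks. The on-treatment checks are "On Days 1, 4, 7, 10 and 14, 2.5 hours after the 1st daily dose of study drug", and the later ones are "On Days 15, 28 and 42 during scheduled visit". The first window therefore holds six checks (Days 1, 4, 7, 10, 14, 15) and the second holds two (Days 28, 42).

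SAP 12.3 defines the first combined value for acuity as the "most worst logMAR score on any Days 1-15" and the second in the same way for Days 28-42. It then says that "the changes in worst logMAR score from Days 1-15 combined to Days 28-42 combined will be summarized", and repeats the construction for vision-impairment class. SAP 12.4 does the same for "the transition of levels of severity of color vision abnormality from Days 1-15 combined to Days 28-42 combined". On the logMAR scale a higher value is worse, so a negative change reads as improvement.

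The SAP also reports each single day against baseline, including Days 14, 15, 28 and 42, by treatment group. It plans no direct within-participant contrast from Day 14 to Day 28 or 42 for any eye measure.

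**The concern.** A maximum taken over more observations tends to be larger. When the first window holds three times as many checks as the second, the worst value falls between windows through measurement variation alone. The pooled contrast is the only planned eye summary that links the on-treatment and follow-up periods within a participant, so a reader will naturally use it to judge recovery.

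The first-in-human trial produced vision-related events, eye symptoms are adverse events of special interest, and the study is meant to select regimens. The error in this contrast leans towards reassurance. It grows if follow-up checks are lost: Day 28 and 42 visits may be held by telephone, which cannot yield the chart or color results.

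**Working it through.** The documents give no figure for this contrast and no visit-to-visit SD or per-check event rate. The SDs, probabilities and correlations below are therefore assumptions, shown over a range.

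**1. Acuity, normal variation around a constant true value.** Let E(k) be the expected maximum of k independent standard normal values, E(k) = ∫ x·k·φ(x)·Φ(x)^(k-1) dx.

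- E(6) = 1.267, E(2) = 0.564, E(1) = 0.
- Expected change = E(2) - E(6) = 0.564 - 1.267 = -0.703 within-person SD of the worst-eye score.
- At SD 0.05: -0.703 × 0.05 = -0.035 logMAR. At SD 0.10: -0.070. At SD 0.15: -0.105. At SD 0: 0.
- One follow-up check lost (six against one): 0 - 1.267 = -1.267 SD.
- Days 1-14 instead of Days 1-15 (five checks, E(5) = 1.163): 0.564 - 1.163 = -0.599 SD.

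**2. Acuity on the SAP's own chart grid.** Simulation of 200,000 participants with two eyes, eight checks and true baseline 0 or 0.10 logMAR. A constant deficit of 0.2 logMAR is added, with independent noise per eye, each result is rounded to the nearest chart value, and the worse eye is taken.

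| Within-eye SD | Mean change | Better / same / worse | Worse than 20/40, Days 1-15 → 28-42 |
|---|---|---|---|
| 0 | 0 | 0 / 100 / 0% | 0% → 0% |
| 0.05 | -0.039 | 41 / 54 / 5% | 44% → 25% |
| 0.10 | -0.058 | 50 / 39 / 11% | 78% → 51% |

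Nothing truly changed in any row.

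**3. Color vision, constant probability p of an abnormal result per check.** With independent checks, the chance of at least one abnormal result is 1-(1-p)^6 in the first window and 1-(1-p)^2 in the second.

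- p = 0.05: 26.5% against 9.8%.
- p = 0.10: 46.9% against 19.0%.
- p = 0.20: 73.8% against 36.0%.

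With correlated checks (beta-binomial, mean 0.10), set s = (1-ICC)/ICC. The chance of no abnormal result in k checks is the product over i = 0..k-1 of (0.9s + i)/(s + i).

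- ICC 0.3: 29.4% against 16.3%.
- ICC 0.5 (s = 1): for two checks 0.9 × 1.9/2 = 0.855, so 14.5%; for six checks 22.3%.

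**4. Alternatives under the same unchanged deficit.** In the simulation, single Day 14 to single Day 28 gives a mean change within 0.0003 logMAR of zero. The worst of Days 14 and 15 against the worst of Days 28 and 42 is within 0.0004, and the mean of all checks per window is within 0.0002.

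**5. Endpoint wording, side by side.**

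- Protocol Tables 2 and 6 and SAP Table 2: change in *mean* acuity score, Days 1-15 combined.
- SAP Table 4 and SAP 12.3: *worst* acuity score, Days 1-15 combined.
- Protocol 9.4.2.2: abnormal acuity and color scores, Days *1-14* combined.
- Protocol Table 9, persistence row: acuity not listed.
- SAP section 8: no change from the protocol's planned analyses.

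**The case against.** **Size and conditions.** The shift exists only if the test varies, is an average, and at plausible SDs is usually less than one chart line. The effect on impairment class needs acuity near a cut-off: entry requires corrected acuity no worse than 20/25 and the normal class runs to 20/40. With no deficit and SD 0.05, the simulated share worse than 20/40 is about 0% in both windows. All of this stands. A reader might infer that an effect persisting unchanged will be reported as recovered. The documents do not support that: a fully reproducible deficit shows no change, and otherwise the picture is of partial improvement.

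**Eye symptoms.** A reader might extend six-against-two to SAP 12.2, which counts "any eye symptom-related AE observed on any Days 28-42". That does not follow. Symptoms are analysed as adverse events, collected continuously from consent to Day 42, and the form in Protocol Appendix 5 asks about problems since the previous check. The number of checks is not the number of chances to record a symptom. It is also true that "The most common AEs associated with HRZE are peripheral neuropathy, optic neuritis, hepatitis, and gastro-intestinal AEs" and that everyone moves to standard treatment on Day 15, so a new symptom at Day 28 or 42 need not be a persisting TBA-7371 effect. But the planned listing gives onset, resolution, dose dates and relationship, readable case by case with about 15 per group.

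**Other output.** Single-day changes from baseline are planned and unaffected, HRZE is displayed and carries the same artefact, and the contrast is descriptive with no test attached. Baseline to the worst of Days 28-42 is shifted the other way (+0.564 SD against a single baseline check), so it would be wrong to infer that every eye table is reassuring. These points limit the consequence. They do not correct the contrast, since nothing planned subtracts the HRZE shift and the single-day group tables do not pair Day 14 with Days 28 and 42 within a participant.

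**Replacing the contrast.** Using Day 14 alone would miss participants affected earlier and normal on Day 14; if abnormal again at Day 28 they would look like new onset. That is right, so the combined transition should stay as a supplement.

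**Conclusion.** The point holds for visual acuity, vision-impairment class and color vision, in the combined-window contrast only. With visit-to-visit variation and no true change, the expected acuity shift is -0.70 within-person SD towards improvement: about -0.035 logMAR at SD 0.05 and -0.07 at 0.10. It is larger if a follow-up check is lost and zero with no variation. For color vision at an assumed 10% per check, the apparent fall is from 46.9% to 19.0% with independent checks and from 22.3% to 14.5% at ICC 0.5. These sizes rest on assumed SDs, rates and correlations; the counts of six and two, the use of worst values and the direction come from the documents.

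This affects a secondary descriptive summary and no hypothesis test. It is still worth correcting, because it is the direct within-participant eye comparison offered for a stated safety objective and it errs towards reassurance.

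**What to change.** - In SAP 12.3 and 12.4, and in the matching endpoint tables, add the within-participant change (acuity) or transition (impairment class, color vision) from Day 14, the last on-drug check, to Day 28 and to Day 42. Make this the main persistence contrast, matching heart rate and blood pressure. Keep the screening or baseline to Days 28 and 42 summaries.
- Keep the Days 1-15 to Days 28-42 transition as a supplementary display for recurrence. Label it as six checks against two, state that it does not measure the amount of recovery, and show how many participants had both, one or no follow-up checks.
- Reconcile the wording: mean or worst acuity score (Protocol Tables 2 and 6 and SAP Table 2 against SAP Table 4 and 12.3); Days 1-14 or Days 1-15 (Protocol 9.4.2.2 against the endpoint tables); and the absence of acuity from the persistence row of Protocol Table 9. Record any resulting change in SAP section 8.
- Optional: tabulate Day 28 and Day 42 eye symptoms by recorded onset and resolution as persisting, recurrent or new.

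The cost is wording and one extra descriptive table. The data are already scheduled for collection.

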3.2. Secondary Objectives and Endpoints

Table 6. Secondary Objectives and Endpoints

Objectives	Endpoints
Bactericidal activity	
Demonstrate the EBA of the first 2 days (screening [“0”] to Day 2) and of the remaining 12 days (Day 2 to Day 14) of 5 dose regimens of TBA-7371 monotherapy and HRZE, as assessed by CFU counts on solid media culture.	
 Slope, i.e. average change per day, from screening (“0”) to Day 2 [0-2] and from Day 2 to Day 14 [BA_{CFU}(2-14)] of the log CFU counts.
Demonstrate the bactericidal activity of 5 dose regimens of TBA-7371 monotherapy and of HRZE, as assessed by alternative methods: 
 time to sputum culture positivity (TTP) in (MGIT) culture LAM assay 	
 Slope of the time to sputum culture positivity (TTP) in the MGIT system from screening (“0”) to Day 14 [BA_{TTP}(0-14)], from screening to Day 2 [BA_{TTP}(0-2)], and from Day 2 to Day 14 [BA_{TTP}(2-14)]. Slope of the log concentration of sputum LAM from screening (“0”) to Day 14 [BA_{LAM}(0-14)], from screening to Day 2 [BA_{LAM}(0-2)], and from Day 2 to Day 14 [BA_{LAM}(2-14)].
Safety	
Assess the adverse event (AE) profile of each dose regimen of TBA-7371 and HRZE over the 14-day treatment period.	
 Frequency from Day 1 through Day 15 of participants with AE and frequency of AEs: overall, by body system, and preferred term; by seriousness, intensity (severity), expectedness and relatedness to study drug.
Assess the impact on eye symptoms, visual acuity and color vision of each dose regimen of TBA-7371 and HRZE over the 14-day treatment period.	
From Day 1 through Day 15:
 
 Frequency of participants with any new (vs. screening) eye symptom in one or both eyes. Mean and frequency distribution of duration of each eye symptom.

Objectives	Endpoints
	
 Mean and frequency distribution of percentage of days with any eye symptom and each of the eye symptoms. Mean/median change in visual acuity score from screening to lowest score during Days 1-15. Frequency of participants with any new color vision abnormalities (tritan, protan, deutan) in one or both eyes and degree of severity (mild, moderate, severe).

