4.4. End of Study Definition

A participant is considered to have completed the study if he/she completes the final visit on Day 42. The end of the study is defined as the date of the last visit of the last participant in the study or last scheduled procedure shown in the SoA for the last participant in the trial.

5. Study Population

Prospective approvals of protocol deviations to enrollment criteria, also known as protocol waivers or exemptions, are not permitted.

Recruitment

Participants will be recruited from communities with known high burden of TB transmission and disease. Various methods of recruitment may be used, such as community information sessions, advertising, referrals, word-of mouth, or solicitation through participants previously known to the clinical site.

Recruitment materials, if any, will be approved by the appropriate Institutional Review Board/s (IRBs) or Independent Ethics Committee/s (IECs). Interested participants will be invited to participate in the informed consent process.

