5.2. Exclusion Criteria

Participants are excluded from the study if any of the following criteria apply.

Medical Conditions and History

- 1. Need for immediate effective anti-TB treatment as judged by the investigator.
- 2. Tested positive for COronaVIrus Disease-19 (COVID-19)/SARS-CoV-2 during the Screening Period with a PCR-based assay.
- 3. Evidence and/or history of extra-thoracic TB (e.g. miliary TB, abdominal TB, urogenital TB, osteoarthritic TB, TB meningitis, ocular TB), as judged by the investigator.
- 4. Evidence and/or history in the last 5 years of one or any combination of the following:
 - a. uveitis;
 - b. color vision deficiency;
 - c. amblyopia;
 - d. visual acuity worse than 20/25 after correction in either eye;
 - e. any known eye disease or prior eye surgery;
 - f. any systemic condition with ocular manifestations (i.e. Marfan, syphilis, diabetes, Beçhet, Vogt-Koyanagi-Harada, Lyme, or chronic inflammatory condition such as sarcoidosis, rheumatoid arthritis, psoriatic arthritis)

5. Evidence and/or history in the last 5 years of clinically significant medical condition(s) as judged by the investigator, including malignancies and unstable or uncontrolled hypertension.
6. Any current medical, psychiatric, occupational, or substance abuse problems that, in the opinion of the investigator, will make it unlikely that the participant will comply with the protocol.
7. For HIV infected participants:
 - a. CD4+ count <350 cells/ μ L, OR
 - b. AIDS-defining opportunistic infection or malignancies (except pulmonary TB).
8. Seated systolic/diastolic blood pressure assessed as vital sign (i.e. not from ECG) is less than 95/40 mmHg or greater than 145/95 mmHg at screening. Out-of-range blood pressure may be repeated twice with at least 5 minutes intervening.
9. Seated heart rate assessed as vital sign (i.e. not from ECG) is lower than 40 beats per minute (bpm) or higher than 110 bpm at screening. Out-of-range heart rate may be repeated twice with at least 5 minutes intervening.
10. A clinically significant ECG abnormality at screening. NOTE: The following can be considered not clinically significant:
 - a. mild first-degree atrio-ventricular block (P-R interval <0.23 sec);
 - b. right or left axis deviation;
 - c. incomplete right bundle branch block;
 - d. isolated left anterior fascicular block (left anterior hemiblock) in young athletic subjects.

Prior/Concomitant Therapy

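### The vision-impairment class tables in SAP 12.3 cannot show acuity loss that stays at 20/40 or better, and no other planned acuity table counts participants who lost acuity.

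*SAP*

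**What the plan says.** Protocol 5.2, criterion 4d, excludes "visual acuity worse than 20/25 after correction in either eye". The opening of Protocol section 5 adds that prospective approvals of deviations from the enrolment criteria, "also known as protocol waivers or exemptions, are not permitted".

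The acuity endpoint in Protocol 3.2 is continuous: "Mean/median change in visual acuity score from screening to lowest score during Days 1-15". Protocol 9.4.2.2 also promises the change over time in how many participants have abnormal acuity.

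SAP 12.3 plans two kinds of summary:

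- **Continuous.** "Worst logMAR score is defined to be the highest value of logMAR scores measured on left and right eyes at a given time point". Descriptive statistics then cover "The changes in worst logMAR score from baseline to Days 1, 4, 7, 10, 14, 15", the two follow-up visits, and the combined windows Days 1-15 and Days 28-42.
- **Categorical.** Frequency and baseline-shift tables of impairment class. Normal is "Equal to or better than 20/40" and Mild is "Worse than 20/40 and equal to or better than 20/70". As to which eye counts, "The highest classification of vision impairment of left and right eyes at the given time point will be selected for the analysis".

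Neither kind compares an eye with its own baseline, and neither counts participants by the amount of acuity lost.

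**The concern.** Eye effects are one of the two most frequent kinds of adverse event reported from the phase 1 study (Protocol 2.3), and acuity is a named secondary safety objective. The class tables are the only acuity displays in SAP 12.3 that count participants. Their first cut lies well below the entry limit, so they are insensitive over the range where modest loss would first appear, and the shift tables should have only one occupied baseline row.

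The SAP treats the other targeted measures differently. Heart rate and blood pressure get counts of participants with a change of 25% or more (SAP 12.5). QTcF gets counts for increases of 31-60 and above 60 msec (SAP 12.6). Acuity has no count based on change.

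The worst-eye rule adds a smaller problem. The eye that supplies the score can differ between baseline and a later visit, so the change need not belong to either eye.

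**Working it through.** **Inputs.** The acuity scale and class limits are from SAP 12.3, the entry limit is from Protocol 5.2, and the group size of 15 is from SAP 6.2. Baseline is the last assessment before the first dose (SAP 9.2). The Day 1 eye test comes 2.5 h after the dose (Protocol Table 3), so baseline acuity is normally the screening test and the entry limit applies to it.

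**1. The SAP's scale.** logMAR = -log10(20/denominator) gives 0.097 for 20/25, 0.176 for 20/30, 0.301 for 20/40 and 0.398 for 20/50. These match the printed 0.10, 0.18, 0.30 and 0.40, and all ten rows agree to two decimals. The SAP does not state the log base. Natural logs would give 0.69 at 20/40, so base 10 is meant.

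**2. Class tables.** Eligible eyes start at 20/20 or 20/25:

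| From | To | logMAR change | Rows lost | Class shift |
|---|---|---|---|---|
| 20/20 | 20/25 | 0.10 | 1 | Normal to Normal |
| 20/20 | 20/30 | 0.18 | 2 | Normal to Normal |
| 20/20 | 20/40 | 0.30 | 3 | Normal to Normal |
| 20/20 | 20/50 | 0.40 | 4 | Normal to Mild |
| 20/25 | 20/30 | 0.08 | 1 | Normal to Normal |
| 20/25 | 20/40 | 0.20 | 2 | Normal to Normal |
| 20/25 | 20/50 | 0.30 | 3 | Normal to Mild |

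**3. Continuous summary.** If an eye falls to 20/40 and the other is no worse, the worst-eye score is 0.30. The recorded change is 0.30 - 0.00 = 0.30 if both eyes began at 20/20, or 0.30 - 0.10 = 0.20 if either began at 20/25. The loss is registered. One such participant in 15 moves the group mean by 0.30/15 = 0.020 or 0.20/15 = 0.013. The group maximum shows it, but not how many participants were affected.

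**4. Worst eye against same eye.** Let b and p be the baseline and later scores of the two eyes.

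- Planned change: W = max(p) - max(b).
- Largest same-eye worsening: S = max(pL - bL, pR - bR).
- S cannot exceed max(p) - min(b), so S - W is at most max(b) - min(b), which is at most 0.10 - 0.00 = 0.10.

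Two examples with eyes starting at 20/20 and 20/25, the second eye unchanged:

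- Better eye to 20/30: S = 0.18, W = 0.18 - 0.10 = 0.08.
- Better eye to 20/25: S = 0.10, W = 0.10 - 0.10 = 0.

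I checked all 2 x 2 x 10 x 10 = 400 left/right combinations of eligible baseline and later table rows. Loss is fully hidden (S above 0, W not above 0) only when the better eye goes from 20/20 to 20/25 and the other eye began at 20/25 and ends at 20/25 or 20/20. The largest under-reading is 0.10.

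**5. Why rows and not logMAR cut-points.** The scale is uneven. A cut at 0.1 misses the one-row loss from 20/25 to 20/30 (0.08), and unrounded it also misses 20/20 to 20/25 (0.097). A cut at 0.2 misses the two-row loss from 20/20 to 20/30 (0.18).

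**The case against.** The strongest reply is that the declared endpoint is the continuous one, and the class tables only supplement it. That is correct. A reader might infer from the class limits that the acuity analysis as a whole would miss real loss. The documents do not support this, because the worst-eye logMAR change in the same section registers loss inside the Normal class.

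A reader might also infer that the worst-eye rule can conceal any amount of loss in the better eye. The entry limit rules that out: under-reading from baseline is capped at 0.10 logMAR, and the only loss fully hidden is one row, ending at a level that still meets the entry criterion. Nor do the documents assign the class tables the role of showing that there is no effect; no acuity hypothesis is tested.

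Other outputs soften the gap. SAP 9.1 provides minimum, maximum and individual listings, and with about 15 participants per group a reader could count from the listings. Protocol 8.3.7 requires acuity results that the investigator considers clinically meaningful to be recorded as adverse events, and SAP 12.1 and 12.2 count those.

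What still stands is that a hand count from listings is not a planned analysis, adverse-event recording depends on judgement, and no planned table states how many participants lost a given amount of acuity.

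**Conclusion.** The point holds for the class frequency and shift tables. They cannot show loss of up to 0.30 logMAR (three rows) from 20/20 or 0.20 (two rows) from 20/25. The continuous summary covers the size of such loss but not the number of participants affected.

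The worst-eye rule is a lesser weakness, worth at most 0.10 logMAR for change from baseline. It also loses the distinction between one-eye and two-eye involvement. In the comparison of Days 1-15 with Days 28-42 it can read zero when one eye recovers and the other falls to the same level, although the change from baseline still shows that loss.

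Two assumptions matter. First, 20/20 is the best score recorded, as in the SAP table; a better recorded baseline would widen the 0.10 bound. Second, recorded baseline acuity is the corrected acuity on which eligibility was judged.

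This is a low-cost improvement to descriptive safety reporting. The primary endpoints, the multiplicity procedure and the sample size are unaffected.

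**What to change.** In SAP 12.3:

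- Compute the change from baseline for each eye against its own baseline, and report the larger worsening.
- Add one table, by treatment group, giving the number and percentage of participants who lost at least 2 and at least 3 rows of the SAP acuity table in either eye, at each eye visit and for Days 1-15 and Days 28-42 combined.
- Keep the impairment classes as a supplementary display.

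The documents set no threshold for acuity loss, so the 2-row and 3-row counts are a proposal and should be fixed in the SAP before the acuity data are summarised.

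The cost is some SAP wording and one table. Each eye is already tested separately (Protocol 8.3.7). The downside is noise: over Days 1-15 the measure takes the worse of two eyes across six visits, so some one-row losses will arise by chance in every group, including HRZE. That is why the counts start at 2 rows.
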